Pilot Study of Natriuretic Versus Standard Doses of Mineralocorticoid Receptor Antagonists in
Heart Failure and Loop Diuretic Resistance in Outpatients

NCT: 02585843

Date 8/30/2015

Study Design

We conducted a pilot, prospective, single-center, double-blind, randomized, placebo controlled trial assessing the effects of high dose spironolactone in addition to intensified loop diuretic therapy vs. standard medical therapy in outpatients with ADHF. Our primary outcome was defined as weight change over the seven day study period. Based on data from a non-randomized intervention study, we aimed to recruit a total sample size of 40 subjects to detect a difference in our primary outcome of weight loss of 1.5kg difference between treatment and control.

On Day 1, all potential subjects were evaluated with complete medical history and physical examination, review of home medications, measurement of vital signs and body weight with a calibrated scale, serum collection for basic metabolic panel, liver function test, biomarkers of congestion, and electrocardiogram. "Imminent hospitalization" was determined by two independent HF specialists to assess the need for hospitalization for intravenous diuretics. Home MRAs were discontinued and potassium supplementation held if baseline serum potassium was >4.0mmol/L. Beta-blockers, ACE-I or angiotensin II receptor blockers were continued at home dose. Loop diuretic dosage was increased by two-fold. Patients were seen at two office visits in total, baseline at day 1 and final visit on day 7. On day 3, participants had serum basic metabolic panel to assess potassium levels and renal function for safety assessment.

Intervention

Enrolled patients were randomly assigned in a 1:1 ratio to high-dose (100mg/day) or standard-dose (25mg/day) spironolactone treatment groups.

Randomization, Allocation and Blinding

Randomization was stratified by sex and EF<45% in blocks of size 4. 2 by 2 randomization was performed via computer model generated by a study investigator. Allocations were concealed via the locked research pharmacy and the research team was blinded to treatment arm. All treatment medications were labeled in a blinded fashion. Subjects received 2 capsules per day (if standard dose: 25mg and placebo, if high dose: two 50mg) dispensed in vials of 2 capsules.

Study Endpoints

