The primary endpoint for the study was defined as change in total body weight at day 7 of the study period. Multiple secondary endpoints from day 1 to 7 were assessed. These included a) changes in dyspnea assessment scores; Visual Analogue Scale and 7-Likert scale, b) signs of congestion (i.e. JVP, peripheral edema and respiratory rales), c) 6MWT, d) serum and urinary creatinine, sodium, potassium and plasma aldosterone and renin activity and biomarkers of congestion and neurohormonal activation, e) furosemide equivalent of treatment loop diuretics doses, e) hospitalization at 30-, 60- and 90-days.

Six-minute walk test was performed per American Thoracic Society guidelines, along with Borg scores for dyspnea and fatigue at day 1 and 7. Serum and urinary creatinine, potassium, and sodium, plasma aldosterone and renin activity, and pro-BNP were assessed at days 1 and 7.

Other biomarkers of peripheral congestion (CD146), inflammation (interleukin-6, tumor necrosis factor- α , endothelin-1) oxidative stress (isoprostane) and endothelial activation (vascular cell adhesion molecule-1) were assessed at day 1 and 7 and analyzed by ELISA or LC-MS.

A data monitoring committee of two independent cardiologists was established to evaluate safety, with a pre-specified stopping rule for harm but not for efficacy. Safety endpoints included changes in serum creatinine levels, eGFR, and the incidence of hyperkalemia during the 7 day treatment period. Safety was assessed by tracking adverse events including new or worsening renal dysfunction, and hyperkalemia. Serious adverse events were defined as death and all-cause hospitalization.

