Pilot Study of Natriuretic Versus Standard Doses of Mineralocorticoid Receptor Antagonists in
Heart Failure and Loop Diuretic Resistance in Outpatients

NCT: 02585843

Date 8/30/2015

Study Endpoints

The primary endpoint for the study was defined as change in total body weight at day 7 of the study period. Multiple secondary endpoints from day 1 to 7 were assessed. These included a) changes in dyspnea assessment scores; Visual Analogue Scale and 7-Likert scale, b) signs of congestion (i.e. JVP, peripheral edema and respiratory rales), c) 6MWT, d) serum and urinary creatinine, sodium, potassium and plasma aldosterone and renin activity and biomarkers of congestion and neurohormonal activation, e) furosemide equivalent of treatment loop diuretics doses, e) hospitalization at 30-, 60- and 90-days.

Six-minute walk test was performed per American Thoracic Society guidelines, along with Borg scores for dyspnea and fatigue at day 1 and 7. Serum and urinary creatinine, potassium, and sodium, plasma aldosterone and renin activity, and pro-BNP were assessed at days 1 and 7. Other biomarkers of peripheral congestion (CD146), inflammation (interleukin-6, tumor necrosis factor- α , endothelin-1) oxidative stress (isoprostane) and endothelial activation (vascular cell adhesion molecule-1) were assessed at day 1 and 7 and analyzed by ELISA or LC-MS.

A data monitoring committee of two independent cardiologists was established to evaluate safety, with a pre-specified stopping rule for harm but not for efficacy. Safety endpoints included changes in serum creatinine levels, eGFR, and the incidence of hyperkalemia during the 7 day treatment period. Safety was assessed by tracking adverse events including new or worsening renal dysfunction, and hyperkalemia. Serious adverse events were defined as death and all-cause hospitalization.

Statistical Analysis

Statistical analyses were performed using SPSS version 23. Continuous variables are presented as mean \pm SD (or median with IQR if not following normal distribution) and categorical variables were summarized as counts (percentages). The χ^2 test or Fisher's exact test (when cell counts were small) were used to compare categorical variables. Paired t-tests and the Wilcoxon rank sum test was used to compare continuous variables pre vs. post intervention within treatment arms. ANOVA was performed to compare continuous variables post-intervention. P< 0.05 considered statistically significant for all comparisons.

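### Binary harms get only a chi-square or Fisher P at 0.05 with about 20 patients per arm; no planned output shows how uncertain the between-arm difference in harm is

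*Protocol*

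**What the plan says.** Under Study Endpoints, the protocol and the SAP both state: "Safety endpoints included changes in serum creatinine levels, eGFR, and the incidence of hyperkalemia during the 7 day treatment period". New or worsening renal dysfunction is tracked as an adverse event, and death and all-cause hospitalization are the serious adverse events. The arms are 100 mg and 25 mg of spironolactone per day (protocol, Intervention).

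Under Statistical Analysis, the SAP summarizes categorical variables as counts with percentages and compares them by chi-square or by Fisher's "exact test (when cell counts were small) were used to compare categorical variables". Continuous variables are compared between arms after the intervention by ANOVA. One threshold covers everything: "P< 0.05 considered statistically significant for all comparisons". There is no separate rule for safety. Neither document plans a risk difference or a confidence interval.

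On size, the protocol says "we aimed to recruit a total sample size of 40 subjects to detect a difference in our primary outcome of weight loss of 1.5kg" and "Enrolled patients were randomly assigned in a 1:1 ratio". No safety endpoint entered the sizing.

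**The concern.** Hyperkalemia, renal events, death and hospitalization are yes/no outcomes, so the SAP's categorical rule governs their comparison. With about 20 patients per arm, that test separates only very large differences from chance. A P above 0.05 is therefore the likely result whether the higher dose is harmless or appreciably harmful, and the P value alone does not tell the reader which.

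This matters because the trial compares two doses of a potassium-retaining drug and is a pilot. Its safety findings would inform any decision to go further. What that decision needs is the range of excess harm still compatible with the data, and the planned analysis does not produce it.

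**Working it through.** **Inputs from the documents.** Total 40, allocation 1:1, so n = 20 per arm (protocol, Study Design and Intervention). Threshold 0.05, and chi-square or Fisher for categorical variables (SAP, Statistical Analysis).

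**Assumptions.** Two-sided tests; no dropout; Fisher when the smallest expected count is below 5 and uncorrected chi-square otherwise (the SAP does not define small); control rates of 0% to 30% (the documents give no expected rate and no potassium threshold for hyperkalemia).

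**The plan's own figure.** The sample size of 40 cannot be reproduced, because the SD and power are not stated. The SD it implies is 1.5 / [(1.960 + z_power) × √(2/20)]. At 80% power this is 1.5 / (2.802 × 0.3162) = 1.69 kg; at 90% power, 1.5 / (3.242 × 0.3162) = 1.46 kg. No power or precision figure exists for safety.

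**Step 1: observed excess of 20 points (4 extra events in 20).** For 0 v 4, two-sided Fisher P = 2 × C(20,4)/C(40,4) = 2 × 4845/91390 = 0.106. The other tables, with the lower-dose arm first:

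| Events (25 mg v 100 mg) | Smallest expected count | Test | P |
|---|---|---|---|
| 0 v 4 | 2 | Fisher | 0.106 |
| 1 v 5 | 3 | Fisher | 0.182 |
| 2 v 6 | 4 | Fisher | 0.235 |
| 3 v 7 | 5 | chi-square | 0.144 (Fisher 0.273) |
| 4 v 8 | 6 | chi-square | 0.168 (Fisher 0.301) |

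None reaches 0.05. By Fisher, significance first appears at 0 v 5 (P = 0.047, a 25-point excess) and 1 v 7 (P = 0.044, a 30-point excess).

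**Step 2: true excess of 20 points.** Power is the sum, over all tables that the rule calls significant with more events at 100 mg, of Bin(a; 20, p₁) × Bin(b; 20, p₀). With p₀ = 0 this reduces to P(at least 5 events | 20, 0.20) = 0.370.

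| True rates | Flagged | Missed |
|---|---|---|
| 0% v 20% | 37% | 63% |
| 5% v 25% | 31% | 69% |
| 10% v 30% | 29% | 71% |
| 20% v 40% | 28% | 72% |
| 30% v 50% | 24% | 76% |

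For a smaller true excess, 5% v 20%, Fisher flags the harm 17% of the time. For a larger one, 5% v 30%, it does so 45% of the time.

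**Step 3: what an interval would show.** The Newcombe limits are d − √[(p₁ − l₁)² + (u₀ − p₀)²] and d + √[(u₁ − p₁)² + (p₀ − l₀)²], where l and u are each arm's Wilson limits.
- 0 v 4: Wilson limits are 8.1% to 41.6% for 4/20 and 0% to 16.1% for 0/20. Lower limit: 20 − √(11.9² + 16.1²) ≈ −0.1 points. Upper limit: 20 + 21.6 = 41.6 points.
- 1 v 5: −3 to +42 points.
- 1 v 6: +0.8 to +47.3 points, although Fisher P = 0.091.
- 0 v 0: 0 ± 16.1 points.

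The last line shows that even with no events in either arm, an excess of about 16 points stays within the interval.

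**The case against.** A reader might infer that the plan treats a non-significant P as proof of comparable safety. The documents do not support that. The SAP names tests and a threshold for calling a result significant. It attaches no meaning to non-significance and sets no equivalence or non-inferiority rule.

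Nor does the P value stand alone. Counts and percentages are planned, so 0/20 v 4/20 would be visible. An independent monitoring committee has a rule, fixed in advance, for stopping on harm. There is a day 3 laboratory check, and potassium, creatinine and eGFR are also available as continuous measures, which usually carry more information than an event count.

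A reader might also infer that any 20-point excess must go undetected. A true excess of that size is usually missed, not always. The observed-excess result also depends on Fisher being used: uncorrected chi-square gives P = 0.035 for 0 v 4 and 0.037 for 1 v 6. Expected counts of 2 and 3.5 make Fisher the usual choice, but the SAP leaves small undefined.

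Finally, low power for harm is common to any 40-patient pilot, and a larger sample is not called for.

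All of this stands and limits the point. The safeguards protect patients and display the data, but they do not quantify the uncertainty of the between-arm difference. Pilot status strengthens the case for intervals, since estimation is what a trial of this size can offer.

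**Conclusion.** The concern holds as a gap in the planned safety output. The only inference planned for binary harms is a P value that, at about 20 per arm, stays above 0.05 for each tabulated 20-point observed excess and misses a true 20-point excess in roughly two-thirds to three-quarters of trials. It is not a finding that the plan declares non-significance safe, or that harm is otherwise unmonitored.

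The figures rest on two-sided testing, full retention, Fisher for expected counts below 5, and the assumed control rates. Dropout would widen the intervals. The primary weight analysis is unaffected. The change is worth making because it alters what the trial can conclude about harm at almost no cost.

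**What to change.** In SAP Statistical Analysis:
- Take the safety endpoints out of the P<0.05 rule.
- For hyperkalemia, new or worsening renal dysfunction, death and hospitalization, report n/N per arm and the risk difference (100 mg minus 25 mg) with a Newcombe 95% CI.
- For changes in potassium, creatinine and eGFR, report the between-arm difference with a 95% CI.
- Make the interval the primary safety output. If a P value is also shown, it is secondary. This settles in advance how to report a table such as 1 v 6, where the interval and Fisher disagree.
- State that a non-significant P is not evidence of comparable safety.

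Do not add a safety margin. With 0 v 0 events the upper limit is already 16.1 points, so a margin of about 16 points or less could not be met at this size.

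The cost is SAP wording and a few more lines of output. Treatment, sample size and data collection do not change. The downside is that the trial can no longer claim no safety difference from a non-significant P.

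### The serious adverse event definition has no life-threatening criterion, so severe hyperkalemia or a severe renal event managed without admission is not classed as serious

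*Protocol*

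**What the plan says.** The last paragraph of Study Endpoints is the same in the Protocol and the SAP. It does four things.

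- It names the safety endpoints: "Safety endpoints included changes in serum creatinine levels, eGFR, and the incidence of hyperkalemia during the 7 day treatment period".
- It names the adverse events to be followed: "Safety was assessed by tracking adverse events including new or worsening renal dysfunction, and hyperkalemia".
- It sets the rule for seriousness: "Serious adverse events were defined as death and all-cause hospitalization".
- It describes oversight: "A data monitoring committee of two independent cardiologists was established to evaluate safety, with a pre-specified stopping rule for harm but not for efficacy".

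The Protocol's Study Design section adds a blood test between the two visits: "On day 3, participants had serum basic metabolic panel to assess potassium levels and renal function for safety assessment". The participants are outpatients: "Patients were seen at two office visits in total, baseline at day 1 and final visit on day 7".

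Neither document gives a potassium threshold, a severity grade, a definition of worsening renal function, or the content of the stopping rule.

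**The concern.** A seriousness rule is meant to separate grave events from minor ones. Here it depends only on whether the patient dies or is admitted. The harms this trial watches are biochemical, and they are looked for in outpatients through a scheduled day 3 panel. If a dangerous result at that point were managed without admission, the plan would give it the same label as a trivial one.

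What is at stake is how the safety results are labelled. Two equally dangerous events would be classed differently according to whether the patient was admitted, which can reflect local practice as much as the event itself. No other stated rule makes up the difference, because hyperkalemia and renal events are not graded.

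**Working it through.** The plan gives no figure to reproduce, so the check is a reading of every safety statement in both documents.

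**Step 1: is the definition closed?** The sentence lists two criteria, death and admission for any cause. It is worded as a definition, not as examples. The Protocol and SAP sentences are identical, so neither document widens the other.

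**Step 2: apply the rule to the harms the plan names.**

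| Hyperkalemia or renal event | Recorded as adverse event or safety endpoint? | Serious under the rule? |
|---|---|---|
| Fatal | Yes | Yes |
| Leads to admission | Yes | Yes |
| Mild, not admitted | Yes | No |
| Life-threatening, not admitted | Yes | No |

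The last two rows receive the same classification, and the last row is the whole of the gap. The middle column is the same in every row, so detection is not the problem.

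**Step 3: does any other stated rule separate the last two rows?**

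- Incidence of hyperkalemia is a count with no threshold or grade.
- Creatinine and eGFR changes are continuous. The SAP's Statistical Analysis section summarises such variables by mean and SD, or by median and IQR. Those are group summaries and need not show one severe case.
- Potassium is measured at days 1 and 7, with a panel on day 3. The size of an abnormality caught at one of these draws could be read from the data, but no rule turns it into a seriousness class.
- The stopping rule for harm is mentioned but not described, so it cannot be relied on in either direction.

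No stated rule does so.

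**Step 4: can the size be computed?** The planned total is 40, randomized 1:1, so 40 / 2 = 20 per arm. One reclassified event would be 1 / 20 = 5 percentage points of an arm. That is the weight of a single event, not a forecast that one will occur. The documents give no rate of severe hyperkalemia or renal failure, and no share of such events managed without admission. The expected number of events in the last row therefore cannot be derived.

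**The case against.** The strongest reply is that nothing is lost. Hyperkalemia, creatinine and eGFR are safety endpoints in their own right, a day 3 panel looks for them, and a committee evaluates safety. The worst cases would often be admitted and so would count. On this view the issue is only a label, in a seven-day pilot of 40 patients. Most of this stands. It limits the point to classification and keeps it modest. It does not remove the point, because the label is the plan's own means of marking grave events, and it omits one kind.

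A reader might infer three stronger things that the documents do not support.

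- **That the monitoring committee would not see these events.** The committee's stated task is to evaluate safety. Nothing says that it reviews serious events only, or that its stopping rule is built on them.
- **That the high-dose arm would look safer than it is.** This would require such events to occur, to be more frequent on the high dose, and not to show in the hyperkalemia and renal results reported alongside. The documents establish none of these.
- **That a probability can be attached.** Any such figure needs an assumed risk of a life-threatening event managed without admission. The documents offer no basis for one, so the answer would only restate the assumption.

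It may also be objected that counting every admission fills the serious-event table with heart failure admissions. But admission for any cause avoids subjective attribution, and randomization balances the background rate in expectation. Listing those admissions separately is a matter of presentation and is not part of this point.

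**Conclusion.** The point holds in a limited form. Both documents use a closed, two-part definition under which a life-threatening hyperkalemia or renal event managed without admission is non-serious, and these are the only specific harms the trial names. This is a stated rule that misclassifies one kind of event, not merely a missing detail.

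The gap concerns seriousness classification alone. Such events are still captured, and those leading to admission or death are classed as serious. Their frequency cannot be quantified from the documents, and no direction of bias is shown. The conclusion rests on one reading, that the definition is exhaustive as written, and on no assumed event rate.

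**What to change.** In Study Endpoints of both documents, replace the definition with wording such as: serious adverse events are death, hospitalization for any cause, and any event that an investigator blinded to arm judges to be life-threatening or medically important, whether or not the patient is admitted. Add that hyperkalemia and renal events meeting this definition are reported to the monitoring committee by arm.

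A criterion based on the need for urgent treatment would be a poor substitute. In outpatients with decompensated heart failure who are being assessed for intravenous diuretics, it would also take in episodes of congestion managed without admission, which are not the harm in question.

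The cost is about one sentence of definition and one of reporting in each document, plus a few more events to adjudicate and report. The added criterion brings in some investigator judgement, and requiring that judgement to be made blind to arm limits the risk of differential classification. It is a reporting definition and changes nothing in treatment or patient care.

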Pilot Study of Natriuretic Versus Standard Doses of Mineralocorticoid Receptor Antagonists in
Heart Failure and Loop Diuretic Resistance in Outpatients

NCT: 02585843

Date 8/30/2015

Study Endpoints

The primary endpoint for the study was defined as change in total body weight at day 7 of the study period. Multiple secondary endpoints from day 1 to 7 were assessed. These included a) changes in dyspnea assessment scores; Visual Analogue Scale and 7-Likert scale, b) signs of congestion (i.e. JVP, peripheral edema and respiratory rales), c) 6MWT, d) serum and urinary creatinine, sodium, potassium and plasma aldosterone and renin activity and biomarkers of congestion and neurohormonal activation, e) furosemide equivalent of treatment loop diuretics doses, e) hospitalization at 30-, 60- and 90-days.

Six-minute walk test was performed per American Thoracic Society guidelines, along with Borg scores for dyspnea and fatigue at day 1 and 7. Serum and urinary creatinine, potassium, and sodium, plasma aldosterone and renin activity, and pro-BNP were assessed at days 1 and 7. Other biomarkers of peripheral congestion (CD146), inflammation (interleukin-6, tumor necrosis factor- α , endothelin-1) oxidative stress (isoprostane) and endothelial activation (vascular cell adhesion molecule-1) were assessed at day 1 and 7 and analyzed by ELISA or LC-MS.

A data monitoring committee of two independent cardiologists was established to evaluate safety, with a pre-specified stopping rule for harm but not for efficacy. Safety endpoints included changes in serum creatinine levels, eGFR, and the incidence of hyperkalemia during the 7 day treatment period. Safety was assessed by tracking adverse events including new or worsening renal dysfunction, and hyperkalemia. Serious adverse events were defined as death and all-cause hospitalization.

Statistical Analysis

Statistical analyses were performed using SPSS version 23. Continuous variables are presented as mean \pm SD (or median with IQR if not following normal distribution) and categorical variables were summarized as counts (percentages). The χ^2 test or Fisher's exact test (when cell counts were small) were used to compare categorical variables. Paired t-tests and the Wilcoxon rank sum test was used to compare continuous variables pre vs. post intervention within treatment arms. ANOVA was performed to compare continuous variables post-intervention. P< 0.05 considered statistically significant for all comparisons.

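### Within-arm pre/post P values are held to the same 0.05 threshold with no descriptive label, although they cannot show the effect of either spironolactone dose

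*SAP*

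**What the plan says.** The Statistical Analysis section of the SAP gives continuous variables two kinds of test. Inside each arm, "Paired t-tests and the Wilcoxon rank sum test was used to compare continuous variables pre vs. post intervention within treatment arms". Across arms, "ANOVA was performed to compare continuous variables post-intervention". One threshold covers both: "P< 0.05 considered statistically significant for all comparisons". Neither kind is labelled descriptive, supportive or primary.

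The Study Design section of the protocol sets out what happens at the visit that supplies the baseline. In the Day 1 paragraph it states: "Loop diuretic dosage was increased by two-fold". No arm is named. The same paragraph says: "Patients were seen at two office visits in total, baseline at day 1 and final visit on day 7". Under Intervention, "Enrolled patients were randomly assigned in a 1:1 ratio to high-dose (100mg/day) or standard-dose (25mg/day) spironolactone treatment groups", so no arm goes without spironolactone.

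The primary endpoint in both documents is change in body weight at day 7. Study Design sizes the trial at 40 patients to detect a 1.5 kg difference in weight loss between the arms.

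**The concern.** A pre/post test inside one arm asks whether patients changed over the week. Here they would be expected to change whatever the spironolactone dose, because they are decompensated outpatients whose loop diuretic has just been doubled. No arm shows what that alone does, so the within-arm change cannot be divided between the loop diuretic and the study drug.

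Two misreadings become possible. If both arms reach P<0.05, the result can be taken to mean that both doses work, when the doubled loop diuretic may explain all of it. If only one arm does, that can be taken as a dose difference, when the arms may have the same true change and fall on either side of the threshold by chance.

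The wording of the SAP makes this more than a remote risk. The endpoint is a change, and the only continuous-data test that explicitly addresses change is the within-arm one. The between-arm ANOVA is described in terms of post-intervention values. The same pair of tests also covers the continuous secondary endpoints, including laboratory values: "Serum and urinary creatinine, potassium, and sodium, plasma aldosterone and renin activity, and pro-BNP were assessed at days 1 and 7".

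**Working it through.** **The plan's own figure.** The total of 40 for a 1.5 kg difference cannot be reproduced, because no SD, power or sidedness is given. Solving backwards with 20 per arm and a two-sided 0.05 t-test, 80% power corresponds to an SD of weight change of 1.65 kg. Check: the noncentrality is 1.5 / (1.65 × √(2/20)) = 2.875, which on 38 df gives power 0.800. For 90% power the SD would be 1.43 kg. I use 1.65 kg as an assumption and vary it below.

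**Inputs.**
- From the documents: 40 patients, 1:1 allocation (20 per arm), threshold 0.05, paired test within each arm.
- Assumed: two-sided testing, no dropout, SD of change 1.65 kg, and the same true mean loss δ in both arms (no dose difference). The documents give no expected shared loss, so a range is shown.

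**Formulas.** For one arm, the paired t statistic has 19 df and noncentrality δ√20 / SD. Let w be the chance that it exceeds the critical value 2.093; significance in the wrong direction is negligible here. The arms are independent, so:
- exactly one arm significant = 2w(1 − w)
- both arms significant = w²

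Worked case, δ = 1.0 kg: noncentrality = 1.0 × 4.472 / 1.65 = 2.710 and w = 0.7296. Exactly one = 2 × 0.7296 × 0.2704 = 0.395. Both = 0.7296² = 0.532.

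| Shared loss (kg) | Given arm significant | Exactly one arm | Both arms |
|---|---|---|---|
| 0.5 | 0.251 | 0.376 | 0.063 |
| 0.75 | 0.488 | 0.500 | 0.238 |
| 1.0 | 0.730 | 0.395 | 0.532 |
| 1.5 | 0.971 | 0.057 | 0.942 |
| 2.0 | 0.999 | 0.002 | 0.998 |

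**Sensitivity to the SD, shared loss 1.0 kg.** With SD 1.2 kg a given arm is significant 0.942 of the time and exactly one arm 0.109. With SD 2.5 kg the figures are 0.397 and 0.479.

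**Between-arm test.** The true difference is zero in every row, so a two-sided 0.05 comparison of the arms rejects 5% of the time whatever the shared loss. A simulation of 40,000 runs at shared losses of 0.5, 0.75 and 1.0 kg gave 0.050 to 0.051.

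**Reading the table.** The two misreadings trade off. Exactly one significant arm is most likely, at one half, near a 0.75 kg shared loss, and fades by 1.5 kg. Two significant arms become close to certain as the shared loss grows.

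**The case against.** The strongest reply is that the plan commits no wrong inference. The SAP never says that a within-arm P value will be read as a dose effect, or that significance in one arm only means that the doses differ. The protocol describes a randomized, double-blind comparison sized on a between-arm difference, so the primary question is plain. This stands, and it limits the point to tests that carry a significance threshold without a label. It does not dispose of it, because the SAP neither ranks the two kinds of test nor words the between-arm one as a comparison of change.

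It is also fair that the chance of exactly one significant arm depends on an undocumented shared loss and is 6% or less from 1.5 kg upward. No single figure in the table can be called typical.

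Three stronger readings are tempting, and the documents do not support them.

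- *The co-interventions bias the comparison of 100 with 25 mg.* The doubling sentence names no arm, and randomization balances what is common to both arms. The opening sentence of Study Design mentions intensified loop therapy alongside the high dose. Taking that as one-arm doubling would fit poorly with the unrestricted instruction and a blinded research team.
- *Prior mineralocorticoid receptor antagonist (MRA) use at home distorts the 25 mg arm by a calculable amount.* The protocol says "Home MRAs were discontinued and potassium supplementation held if baseline serum potassium was >4.0mmol/L". The number of users and their doses are not given, and the potassium condition may govern the stopping of the MRA as well as the supplement. A power figure would rest on stacked assumptions, so none is offered.
- *The 80% power behind the assumed SD carries over to the SAP's ANOVA.* That SD refers to weight change. An unadjusted ANOVA of day-7 weight also carries the spread in body weight between patients, so its power need not be 80%, although its 5% error rate holds.

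**Conclusion.** The point holds and is minor. Significance inside an arm is not evidence about 25 or 100 mg, because the loop diuretic is doubled at the baseline visit and no arm is free of spironolactone. That conclusion needs only the documents. Its size rests on 20 per arm, two-sided testing, an assumed SD of 1.65 kg and an assumed common loss. With no dose difference and a shared loss of 0.5 to 2.0 kg, a given arm is significant 25 to 100% of the time, against 5% for the between-arm comparison.

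A reader might infer that the plan intends to draw dose conclusions from these tests, or that the randomized comparison is compromised. Neither follows. What is missing is a statement of which comparison carries the conclusion, together with a between-arm analysis worded to match a change endpoint.

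**What to change.** Replace the within-arm testing sentence and the ANOVA sentence in the SAP with wording such as:

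> Changes from day 1 to day 7 within each arm are descriptive: mean change with 95% CI, or median with IQR. No significance is claimed for them, and significance in one arm but not the other is not taken as a dose difference. Conclusions rest on the comparison between arms. Day-7 body weight is compared between arms with adjustment for Day 1 body weight; the other continuous endpoints are analysed in the same way, each adjusted for its own Day 1 value.

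For weight, this adjusted model gives the same arm difference as a model for change with the same adjustment, so it answers the stated primary endpoint.

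The cost is small. Day 1 weight and the other baseline values are already collected, so no visits, patients or data are added. Within-arm P values are no longer reported, and each model uses one further degree of freedom (residual 37 instead of 38 with 40 patients). An adjustment for home MRA dose is not recommended on the information given.
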